**Duration of Study:** It is expected that approximately 24 months will be required to complete enrollment in the study. Subjects may discontinue from treatment because of disease progression, unacceptable toxicity, withdrawal of consent, or at the discretion of the Investigator. The last visit for each subject will be defined as the follow up visit which is no less than 90 days after the subject’s end-of-treatment visit. The last visit is either 90 days after last dose or whenever a study drug related toxicity has resolved, stabilized, or been deemed reversible, whichever is latest. The end of the trial will occur on the last visit of the last patient.

**Number of Subjects:** A total of up to 36 subjects are expected to be treated on the study.

**Study Population:** Male and female subjects  $\geq 18$  years of age with a histologic or cytologic diagnosis of unresectable Stage III or Stage IV melanoma and who meet the eligibility criteria (see Sections 3.2.1 and 3.2.2) will participate in the study.

**Investigational Product(s), Dose and Mode of Administration, Duration of Treatment with Investigational Product(s):** Panobinostat is available as 5, 10, 15, and 20 mg capsules and will be administered orally. Ipilimumab is available as sterile dose formulation at 5 mg/mL and will be administered intravenously (IV) as an infusion over 90 minutes. Ipilimumab is not to be administered as an IV push or bolus injection. Panobinostat will be administered at 5, 10 mg, 15 mg, or 20 mg thrice weekly in combination with ipilimumab administered at a dose of 3 mg/kg according to the dose schedule in Table 1. Panobinostat doses beyond 20 mg PO TIW may be considered if appropriate as outlined under study design.

**Study Assessments and Primary Endpoints:** Subjects will be required to visit the investigator’s office or clinic for physical examinations, vital sign measurements, ECOG performance status evaluation, adverse event

assessment, laboratory testing, pharmacodynamic (PD) sample collection, and administration of study drug as per the study schedule.

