##### **4.1.1.1 Ipilimumab (BMS-734016)**

Study drug is to be administered and prepared according to the package insert as described below.

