#### Preparation of Solution

- Allow the vials to stand at room temperature for approximately 5 minutes prior to preparation of infusion.
- Withdraw the required volume of YERVOY and transfer into an intravenous bag.
- Dilute with 0.9% Sodium Chloride Injection, USP or 5% Dextrose Injection, USP to prepare a diluted solution with a final concentration ranging from 1 mg/mL to 2 mg/mL. Mix diluted solution by gentle inversion.
- Store the diluted solution for no more than 24 hours under refrigeration (2°C to 8°C, 36°F to 46°F) or at room temperature (20°C to 25°C, 68°F to 77°F).
- Discard partially used vials or empty vials of YERVOY.

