#### Administration Instructions

- Do not mix YERVOY with, or administer as an infusion with, other medicinal products.
- Flush the intravenous line with 0.9% Sodium Chloride Injection, USP or 5% Dextrose Injection, USP after each dose.
- Administer diluted solution over 90 minutes through an intravenous line containing a sterile, non-pyrogenic, low-protein-binding in-line filter.

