#### Dose, Volume and Rate Calculations

Total dose should be calculated as follows:

Subject body weight in kg x 3 mg = total dose, mg

Total infusion volume should be calculated as follows: Total dose in mg divided by 5 mg/mL = infusion volume, mL

Rate of infusion should be calculated as follows: Infusion volume in mL divided by 90 minutes = rate of infusion, mL/min

For example, a subject weighing 114 kg (250 lb) and designated to receive ipilimumab at a dose of 3 mg/kg would be administered 342 mg of ipilimumab (114 kg x 3 mg/kg = 342 mg) with an infusion volume of 70 mL (342 mg divided by 5 mg/mL = 70 mL) at a rate of approximately 0.77 mL/min (70 mL divided by 90 minutes) in 90 minutes.

Ipilimumab (BMS-734016) Injection (5 mg/ml), must be stored refrigerated (2 - 8°C) with protection from light. Ipilimumab may be stored (5 mg/ml) in DEHP free IV infusion bags for up to 24 hours at room temperature or refrigerated (2°C - 8°C). This would include any time in transit and the total time for infusion. Drug must be completely delivered to the subject within 24 hours of preparation.

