#### **4.1.2 Handling and Dispensing**

The investigational pharmacist will ensure that the study drug is stored in accordance with the environmental conditions (temperature, light, and humidity) as determined by the package insert. If concerns regarding the quality or appearance of the study drug arise, do not dispense the study drug and contact the sponsor immediately.

Panobinostat 5 mg, 10 mg, 15 mg and 20 mg capsules must be stored below 25°C, in very tight packaging with water permeation <0.5 mg/day/liter, protected from light. Ipilimumab

(BMS-734016) Injection (5 mg/ml), must be stored refrigerated (2 - 8°C) with protection from light. Ipilimumab may be stored (5 mg/ml) in DEHP free IV infusion bags for up to 24 hours at room temperature or refrigerated (2°C - 8°C). This would include any time in transit and the total time for infusion. Drug must be completely delivered to the subject within 24 hours of preparation.

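### Section 4.1.1.1 takes the ipilimumab infusion volume and rate from the undiluted 5 mg/mL stock, although it requires infusion of a 1–2 mg/mL dilution; secondarily, section 4.3.6 and Table 4.3 disagree on dose reduction at level 1

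*Combined protocol and SAP*

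**What the plan says.** **Infusion volume and rate.** The Synopsis, under Investigational Product(s), gives the supplied strength: "Ipilimumab is available as sterile dose formulation at 5 mg/mL". Section 4.1.1.1 opens with "Study drug is to be administered and prepared according to the package insert as described below". Under Preparation of Solution, the drug is withdrawn from the vials and diluted "to prepare a diluted solution with a final concentration ranging from 1 mg/mL to 2 mg/mL". Under Administration Instructions: "Administer diluted solution over 90 minutes through an intravenous line".

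Under Dose, Volume and Rate Calculations, the same section then gives "Total dose in mg divided by 5 mg/mL = infusion volume, mL" and "Infusion volume in mL divided by 90 minutes = rate of infusion, mL/min". Its worked example is a 114 kg subject at 3 mg/kg (342 mg), with an "infusion volume of 70 mL (342 mg divided by 5 mg/mL = 70 mL") and a rate of about 0.77 mL/min. The storage text that follows, repeated in section 4.1.2, says "Ipilimumab may be stored (5 mg/ml) in DEHP free IV infusion bags for up to 24 hours".

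Section 4.3.2 asks for whatever rate completes the infusion in 90 minutes.

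**Level 1 dose reduction.** Section 4.3.6 sends a first hematologic or non-hepatic non-hematologic DLT to the reductions in Table 4.3. A later bullet in that section says that patients on dose level 1 are not reduced after a DLT. The cohort 1 row of Table 4.3 gives one reduction (ipilimumab from 3 to 1 mg/kg, panobinostat unchanged at 5 mg) and then off study.

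**The concern.** The calculation block treats the vial concentration as if it were the concentration in the bag. A volume obtained from 5 mg/mL tells the pharmacist how much to draw up. It does not tell the nurse how much fluid will run through the line once diluent has been added. The rule covers every ipilimumab infusion, up to four per patient. Staff who dilute as instructed have to set aside the printed infusion volume and rate and work out their own.

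In section 4.3.6, a cohort 1 patient with a qualifying cycle 1 DLT could be given different instructions for cycle 2, depending on whether the bullet or the table is followed. The bullet also does not say whether a patient who is not reduced restarts at 3 mg/kg or stops.

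**Working it through.** **Inputs.** Stock 5 mg/mL (Synopsis). Final concentration 1 to 2 mg/mL, and diluted solution given over 90 minutes (section 4.1.1.1). Example subject: 114 kg at 3 mg/kg (section 4.1.1.1).

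**The plan's own figures**
- Dose: 114 × 3 = 342 mg.
- Volume by the printed formula: 342 / 5 = 68.4 mL. The plan prints 70 mL, which is consistent with rounding up.
- Rate: 68.4 / 90 = 0.76 mL/min, or 70 / 90 = 0.78 mL/min. The plan prints about 0.77 mL/min.

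These figures reproduce only with undiluted drug. Putting 342 mg in 70 mL gives 342 / 70 = 4.9 mg/mL, outside the required 1–2 mg/mL.

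**A bag that meets the dilution rule**

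| | At 2 mg/mL | At 1 mg/mL |
|---|---|---|
| Withdraw from vials | 342 / 5 = 68.4 mL | 68.4 mL |
| Infusion volume | 342 / 2 = 171 mL | 342 / 1 = 342 mL |
| Diluent added | 171 − 68.4 = 102.6 mL | 342 − 68.4 = 273.6 mL |
| Rate over 90 minutes | 171 / 90 = 1.9 mL/min | 342 / 90 = 3.8 mL/min |

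**Ratio for any weight or dose.** (dose / 2) / (dose / 5) = 2.5, and (dose / 1) / (dose / 5) = 5. The 90 minutes cancel, so the rate is wrong by the same factor as the volume.

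**The storage sentence.** A bag held at 5 mg/mL fits the printed formulas but not the dilution step. It belongs to the same inconsistency and does not resolve it.

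**Reach of the level 1 conflict.** Ipilimumab is given on days 1 and 22 of two induction cycles, so 2 × 2 = 4 infusions. Section 4.3.6 ties restart after a DLT to the next cycle, and section 3.1 makes maintenance panobinostat alone. The conflict can therefore change ipilimumab only after a cycle 1 DLT, and only for the two cycle 2 infusions. Several DLTs drop out because section 4.3.6 removes the patient: hepatic DLTs, Grade 3 or higher irAEs, irreversible Grade 4 organ dysfunction and anaphylaxis. Section 4.3.7.1 stops study drug after a Grade 3–4 infusion reaction. What remains is other DLTs, such as hematologic ones.

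**The case against.** The best defence is that this is a labelling slip. Dose / 5 mg/mL is the correct amount for the withdrawal step, the milligram dose is right, the section refers to the package insert, and the 90-minute duration appears in the Synopsis and in sections 4.1.1.1 and 4.3.2. Most of this stands, and it limits the consequence. It does not make the text correct: the calculation block calls the quantity the infusion volume, derives the rate from it, and repeats both in the example.

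A reader might infer that patients would be under-dosed. At the printed settings, 90 minutes would deliver about 70 mL of diluted solution, or 70–140 mg, which is 20–41% of 342 mg; emptying the bag at 0.77 mL/min would take about 222 minutes (171 / 0.77) to 444 minutes (342 / 0.77). The documents do not support expecting this, because it requires staff to run the printed rate and also ignore the repeated 90-minute target. A reader might also count 70 against 68.4 mL as a separate arithmetic error. It is a 1.6 mL rounding in an example that states the dose exactly.

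On level 1, Table 4.3 also serves reductions that are not DLTs. Table 4.2 orders a one-level reduction for some drug-related QTcF prolongation, so the cohort 1 row could have a purpose even if DLTs are excluded. That is a fair partial reconciliation. It is not complete, because section 4.3.6 itself refers first DLTs to Table 4.3. A reader might conclude that the table should prevail and that level 1 patients should be retreated at 1 mg/kg. The documents do not support that default. The same bullet allows level 2 one reduction and removes the patient at a second DLT, so by analogy it may mean removal at the first DLT for level 1. Moreover, the table lowers only ipilimumab, whereas section 1.4.3 names thrombocytopenia as a major toxicity of panobinostat.

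**Conclusion.** The volume and rate rule is wrong as written, with modest practical risk. For any bag that meets the 1–2 mg/mL requirement, the stated infusion volume and rate are too small by a factor of 2.5 to 5, whatever the weight or assigned dose. This rests only on the stock strength and the dilution range, both stated in the protocol.

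The level 1 conflict is real but narrow: at most two of four ipilimumab infusions, in the few cohort 1 patients whose cycle 1 DLT does not itself require removal. The documents do not show which rule the sponsor intends.

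A reader might infer that either point disturbs the dose-finding results. Neither does: the DLT definitions, the escalation table, the sample size of 36 and the planned analyses are unchanged. The correction is still worth making, because these are drug-preparation and retreatment instructions in a trial whose primary objective is safety.

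**What to change.** In section 4.1.1.1, replace the volume and rate formulas with three:
- withdrawal volume = dose / 5 mg/mL;
- infusion volume = dose / final concentration (1–2 mg/mL);
- rate = infusion volume / 90 minutes.

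Update the worked example to about 68.4 mL withdrawn and 171–342 mL infused at 1.9–3.8 mL/min.

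In the bag-storage sentences of sections 4.1.1.1 and 4.1.2, change only the 5 mg/mL figure to the diluted concentration. Keep the DEHP-free bag requirement, the 24-hour limit that includes transit and infusion time, and the requirement for complete delivery within 24 hours of preparation. The shorter storage rule under Preparation of Solution lacks these safeguards, so it should not replace them.

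In section 4.3.6 and Table 4.3, the sponsor should choose one level 1 rule and state it in both places. One option is a single reduction to ipilimumab 1 mg/kg with panobinostat 5 mg, then off study. The other is off study at the first DLT, with the cohort 1 row marked as applying only to reductions that are not for a DLT.

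The cost is protocol wording only, with no added patients and no change to the DLT rules or the analyses.

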#### **4.1.1.2 PANOBINOSTAT (LBH-589)**

The drug product will be provided by Novartis and is an immediate-release solid oral dosage form capsule. The hard gelatin capsules contain the active substance Panobinostat lactate salt at dosage strengths of 5 mg, 10 mg, 15 mg and 20 mg as anhydrous free base. The inactive ingredients are: mannitol, microcrystalline cellulose, pregelatinized starch and magnesium stearate. An aqueous granulation and blending process produces the capsule content. The 5 mg, 10 mg, 15 mg, and 20 mg capsules are packaged in high-density polyethylene (HDPE) bottles with an induction seal and plastic CR closure. The current storage condition for all capsules strengths is: Do not store above 25°C. The retest date for the capsule formulations will be assigned based on available stability data.

#### **4.1.2 Handling and Dispensing**

The investigational pharmacist will ensure that the study drug is stored in accordance with the environmental conditions (temperature, light, and humidity) as determined by the package insert. If concerns regarding the quality or appearance of the study drug arise, do not dispense the study drug and contact the sponsor immediately.

Panobinostat 5 mg, 10 mg, 15 mg and 20 mg capsules must be stored below 25°C, in very tight packaging with water permeation <0.5 mg/day/liter, protected from light. Ipilimumab

(BMS-734016) Injection (5 mg/ml), must be stored refrigerated (2 - 8°C) with protection from light. Ipilimumab may be stored (5 mg/ml) in DEHP free IV infusion bags for up to 24 hours at room temperature or refrigerated (2°C - 8°C). This would include any time in transit and the total time for infusion. Drug must be completely delivered to the subject within 24 hours of preparation.

## 4.2 Method of Assigning Subject Identification

This is an open-label study. All enrolled subjects will be assigned a subject number, starting with 00001. After it has been determined that the subject meets all eligibility criteria, the investigator (or designee) will register the subject by following the enrollment procedures established at Moffitt. The following information is required for registration:

- Date of birth
- Gender
- Diagnosis
- Date of informed consent
- Planned date of 1st dose

The subject number will be assigned once the subject signs informed consent. Subject numbers will be assigned in the order of enrollment within 3 days prior to Day 1 of Cycle 1 dosing. Subjects who do not complete the DLT observation period for reasons other than drug-related toxicity will be replaced. Replacement subjects will receive the same treatment but will be assigned a new subject number.

## 4.3 Selection and Timing of Dose for Each Subject

As described under Study Design (Section 3.1), panobinostat will be administered orally concurrently in combination with intravenous ipilimumab. For each arm, treatment will be divided into induction and maintenance phases.

### 4.3.1 Study Treatments During Dose Escalation

Subjects will be enrolled in successive cohorts of 3. An initial cohort of 3 subjects will be enrolled at a given dose level, and additional cohorts of at least 3 subjects will be added based on the design as outlined in Section 3.1. The first cohort will receive panobinostat orally at a dose of 5 mg PO TIW; ipilimumab will be administered IV at 3 mg/kg. Subsequent dose levels of panobinostat and ipilimumab will be increased according to the schedule in Table 4.1.

**Table 4.1 Dose Escalation regimen for Panobinostat and Ipilimumab**

Dose Cohort	Panobinostat Dose	Ipilimumab Dose
1	5 mg po TIW	3 mg/kg
2	10 mg po TIW	3 mg/kg
3	15 mg po TIW	3 mg/kg
4	20 mg po TIW	3 mg/kg
-1	5 mg po TIW	1 mg/kg

Additional dose levels of panobinostat beyond the 20 mg PO TIW dose cohort may be added as appropriate, although it is expected that all subsequent doses will be no more than 33%

higher than the preceding dose (eg, from 20 mg PO TIW to 25 mg PO TIW). Start of induction cycle 1, Day 1 for the first 3 subjects should be separated by at least 1 day. During the DLT observation (within 84 days of initiation of study therapy), subjects, who for reasons other than study-drug related toxicity, either miss 1 or more of their scheduled doses of ipilimumab, or miss more than 10% of their scheduled Q12 hour doses of panobinostat, or do not complete the first induction cycle, will not be considered evaluable for safety for the purposes of dose escalation and will be replaced.

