# **3 INVESTIGATIONAL PLAN**

## **3.1 Study Design and Duration**

This is a Phase 1 open label study of panobinostat administered in combination with ipilimumab. Subjects with unresectable Stage III or Stage IV melanoma who meet the eligibility criteria will undergo screening evaluations within 28 days prior to initiation of study therapy. The study will consist of a dose escalation assessment of the safety and tolerability of oral panobinostat administered concurrently in combination with ipilimumab. Treatment will be divided into induction with ipilimumab and panobinostat and a maintenance phase with panobinostat alone consistent with the general principles of ipilimumab therapy. It is anticipated that this evaluation will enable selection of the RP2D of this combination for further clinical testing. A study schematic is presented below:

Each treatment cycle will be 42 days (6 weeks) during the induction phase, and 84 days (12 weeks) during the maintenance phase. Panobinostat will be administered orally TIW on Days 1-42 of each 42 day treatment cycle. Ipilimumab will be administered intravenously (IV) once every 3 weeks on Days 1 and 22 of each treatment cycle. The induction phase will last for up to 2 treatment cycles. During the maintenance phase, panobinostat will be administered orally TIW on Days 1-84 of each 84 day treatment cycle. Subjects will continue maintenance panobinostat treatment with their designated combination dose regimen until progression of disease, discontinuation due to toxicity, withdrawal of consent or any other reason as specified in Section 3.4.

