**There will be no intra-subject dose escalation.** Decisions regarding dose escalation between cohorts will be guided by the incidence of drug-related dose limiting toxicities (DLTs) occurring within 84 days (12 weeks; through Day 42 of induction cycle 2) of initiation of study therapy. If three patients complete their 84 day period of treatment without DLT, then at least three additional patients must exceed 9 weeks without MTD being reached to be able to dose escalate. This DLT observation interval is based upon inclusion of the known median times to onset of common immune-related adverse events attributed to ipilimumab (see Section 4.3.5.1) and allows for a substantial amount of time for unexpected toxicities with the combined administration of panobinostat and ipilimumab to emerge. Subjects who do not complete the DLT observation period for reasons other than drug-related toxicity will be replaced. One of the following five decisions will be made at the end of the DLT period for each cohort of 3 subjects based on the number of DLT's observed:

- S: stay at the same dose and enroll a cohort of 3 more subjects at that dose
- E: escalate to the next higher dose by enrolling 3 more subjects
- D: de-escalate to the lower dose, and enroll 3 more subjects at the lower dose, or
- DU: declare the current dose as unacceptable and unsafe, de-escalate to the lower dose, and enroll 3 more subjects at the lower dose
- C: Study completed and dose is declared to be the MTD

Decisions S or E are allowed by the design if determined that the corresponding doses are safe based on the target toxicity. Decisions D or U are based on evidence of exceeding predetermined toxicity. With a target toxicity rate of 18%, allowing any dose with estimated  $P_T$  in the (17%, 19%) interval to be selected as the MTD in this study, and with a maximum fixed total of 36 subjects at the dose escalation phase in each arm, the algorithm for dose escalation decisions based on possible total number of subjects at each dose cohort is described in Table 3.2 below.

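### The DLT-evaluability rule in Section 4.3.1 rests on a 12-hourly panobinostat schedule found nowhere else in the protocol, and its completion limb disagrees with the 84-day replacement rule

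*Combined protocol and SAP*

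**What the plan says.** The paragraph after Table 4.1 (Section 4.3.1) opens with the full window: "During the DLT observation (within 84 days of initiation of study therapy". It then removes from the escalation count, and replaces, subjects who meet any one of three conditions for reasons other than study-drug toxicity:

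- ipilimumab: "either miss 1 or more of their scheduled doses of ipilimumab"
- panobinostat adherence and, as the third condition, completion: "miss more than 10% of their scheduled Q12 hour doses of panobinostat, or do not complete the first induction cycle"

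Section 3.1 gives the schedules. For panobinostat: "Panobinostat will be administered orally TIW on Days 1-42 of each 42 day treatment cycle". For ipilimumab: "Ipilimumab will be administered intravenously (IV) once every 3 weeks on Days 1 and 22 of each treatment cycle". Table 4.1, directly above the evaluability sentence, also lists panobinostat as TIW.

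Section 3.1 has its own replacement rule: "Subjects who do not complete the DLT observation period for reasons other than drug-related toxicity will be replaced". The synopsis and Section 4.2 repeat it. Sections 3.1 and 4.3.3 set the DLT period at 84 days, through Day 42 of induction cycle 2. Section 3.1 adds a further condition for escalating after three DLT-free completers: at least three more patients must have passed 9 weeks.

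**The concern.** The primary objective is to define DLTs, the MTD and the RP2D. Tables 3.2 and 8.1 turn a DLT count over a number of subjects into an action. In a cohort of three, one subject changes that action: 0 DLTs means escalate, 1 means stay, and 2 means declare the dose unacceptable. The rule on who counts therefore has to be usable and the same everywhere.

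There are three weaknesses.

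- The adherence limb refers to 12-hourly dosing, which no other part of the protocol describes, and it concerns the drug being escalated.
- The completion limb asks for less than the replacement rule does. Counting a DLT-free subject who left early pushes the observed DLT rate down.
- No text says that a subject who has had a DLT always stays in the count.

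**Working it through.** **Window.** Two cycles × 42 days = 84 days = 12 weeks × 7 days. The plan's figure reproduces.

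**Adherence limb.** Inputs: TIW dosing (Section 3.1), the 84-day window, and the 10% limit (Section 4.3.1).

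- Scheduled doses on TIW: 12 × 3 = 36. Ten per cent is 3.6, so a fourth missed dose would exclude a subject.
- Scheduled doses if given every 12 hours: 84 × 2 = 168.
- Literal reading: a fully adherent subject takes 36/168 = 21.4% and misses 132/168 = 78.6%. That is above 10%, so nobody is evaluable.
- Void reading (no 12-hourly dose is scheduled, so none can be missed): there is no adherence criterion for panobinostat.

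**Completion limb.** Ipilimumab on Days 1 and 22 of two 42-day cycles falls on study Days 1, 22, 43 and 64. Take a subject who leaves for a reason other than toxicity, having had every dose up to the last study day L, with L before 84. Sections 3.1 and 4.2 replace that subject whatever L is. Under Section 4.3.1 alone:

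| Adherence limb | Subject still evaluable if | L on which the rules disagree |
|---|---|---|
| Void | L ≥ 64 (fourth ipilimumab dose given; cycle 1 complete) | 64 to 83 (20 days) |
| Read as TIW | L ≥ 64 and at most 3 doses scheduled after L | 75 to 83 (9 days) |

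The second row assumes dosing on days 1, 3 and 5 of each week. The last doses are then Days 71, 73, 75, 78, 80 and 82, and leaving after Day 75 misses three. Patterns 1-3-6 and 1-4-6 start the range at Day 76. If completion meant the 84-day period in both places, no day would be classified differently.

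The 9-week condition is a third threshold, at 9 × 7 = 63 days.

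**Effect on the decision (illustration).** Assume the cohort contains one DLT-free early leaver, the other subjects have independent true DLT rate p, and a replacement also has rate p.

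- N = 3, escalate at 0 DLTs: counted (1 − p)²; replaced (1 − p)³.
- N = 6, escalate at 0 or 1 DLT: counted P(Bin(5, p) ≤ 1); replaced P(Bin(6, p) ≤ 1).

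| p | N = 3 counted | N = 3 replaced | N = 6 counted | N = 6 replaced |
|---|---|---|---|---|
| 0.10 | 0.810 | 0.729 | 0.919 | 0.886 |
| 0.18 | 0.672 | 0.551 | 0.778 | 0.704 |
| 0.25 | 0.562 | 0.422 | 0.633 | 0.534 |
| 0.33 | 0.449 | 0.301 | 0.468 | 0.358 |

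At the 18% target: 0.82² = 0.672 and 0.82³ = 0.551. Every shift favours escalation.

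**Subject with a DLT.** Section 4.3.6 allows treatment to restart after a first hematologic or non-hepatic non-hematologic DLT that has resolved to Grade 1 or less. If that subject then leaves before Day 84 for, say, withdrawn consent, the reason is not drug-related toxicity, and Sections 3.1 and 4.2 literally require replacement. A 1/3 (stay) could then become 0/3 (escalate).

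**The case against.** **The 12-hourly wording is an obvious slip that staff would read as TIW.** They probably would. But the sentence is an operative rule, its two literal readings give opposite results, and the choice of reading moves the completion gap from 20 days to about 9.

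**The completion rules can be applied together.** Section 4.3.1 lists who is not evaluable and does not say that everyone else is. Adding the stricter rule gives a coherent 84-day denominator. This largely stands, and it is why the point is inconsistency rather than a wrong denominator. However, only Section 4.3.1 defines evaluability for dose escalation, so it could reasonably be used alone.

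**Leaving treatment does not end observation.** Section 3.4 requires follow-up, Section 5.3 documents SAEs for 90 days after discontinuation, and Section 6.2.1 collects drug-related nonserious events to the day-90 visit. This stands: Days 64 to 83 are not necessarily unobserved, although the subject is then off treatment. Scheduled tumour assessments at weeks 6 and 12 also make progression-driven departures between those visits less likely.

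**Table 8.1 defines N as subjects treated, not evaluable.** True, and it is one more loose end, since the replacement rules only make sense if the count excludes those replaced.

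Some stronger readings are tempting but not supported:

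- That Section 4.3.1 simply uses a 42-day window. Its sentence is framed by 84 days, and its ipilimumab limb reaches Day 64.
- That 10% of 168 allows 16 of the 36 real doses (44%) to be missed. The text limits a percentage of scheduled doses and grants no fixed allowance.
- That DLTs are generally lost. Hepatic DLTs and Grade 3 or greater irAEs lead to removal for toxicity, which the replacement rules do not touch.

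**Conclusion.** The concern holds in a bounded form. The adherence limb cannot be applied as written, and the denominator for dose escalation is not uniquely defined. The completion rules disagree only for a last study day of 64 to 83, or about 75 to 83 if adherence is read as TIW with the dosing days assumed above.

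Where one such DLT-free leaver is counted rather than replaced, the chance of 0 DLTs in 3 rises by 0.121 at a true rate of 18% (0.672 − 0.551), and by 0.081 to 0.148 over assumed rates of 10% to 33%. These figures are conditional on such a leaver being present. They are not the average bias over the trial, because the documents give no frequency of early departure and the leaver has already been on study for at least 64 of the 84 days.

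The DLT-retention gap is narrow: a resolved DLT, resumed treatment, then departure for an unrelated reason. It is nonetheless unprotected. A reader might conclude that the DLT denominator is simply wrong. The documents do not support that, because the strict 84-day rule also stands in them.

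**What to change.** - Reconcile the adherence limb in Section 4.3.1 with the dosing schedule stated elsewhere. If the thrice-weekly schedule stands, state the limit as a percentage of scheduled TIW doses in the DLT window.
- Give one completion requirement in the same words in the synopsis and Sections 3.1, 4.2 and 4.3.1, and reconcile the 9-week condition in Section 3.1 with it.
- State that any subject with a DLT in the window is counted and not replaced, whatever the later reason for leaving.
- Make the definition of N under Tables 3.2 and 8.1 match the resulting evaluable set.

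The cost is a few sentences, with no new data collection. If the 84-day requirement is the one kept, a few subjects may be replaced who would have counted under Section 4.3.1 alone.
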